10.11. Subject Withdrawal or Discontinuation

Participation in this study is voluntary and the study subject has the right to discontinue participation at any time without penalty or loss of benefits to which the subject is otherwise entitled. A withdrawn subject will be treated according to standard of medical care and will not be replaced. Subjects will be included in the analyses up to the time that consent was withdrawn.

Subjects may also be withdrawn from the study at the discretion of the Investigator if the patient's well-being is jeopardized by continuation of the study.

If a subject chooses to end his or her study participation or if a subject is removed from the study at the Investigator's discretion, the date, circumstances and the reason for termination must be documented both in source documents and on the appropriate eCRF. No data obtained after withdrawal of consent will be recorded on eCRF.

The study site will make every effort to have all subjects complete the follow-up visit schedule. A subject will not be considered lost to follow-up unless all efforts to obtain compliance are unsuccessful. At a minimum, the effort to obtain follow-up information must include 3 attempts to make contact via telephone and if contact via phone is not successful, a traceable letter from the investigator should be sent to the subject's last known address, a copy of which should be maintained in the subject's study record. If both telephone and mail contact efforts are unsuccessful, the subject's personal physician (if subject confirmed agreement in consent) should be contacted to verify the subject's safety information and vital status (alive or deceased). Subject will then be deemed lost to follow up. All contact efforts to obtain follow-up must be documented in the subject's medical records.

If a subject discontinues the study at any time or is withdrawn from the study early, they should continue to be followed as per standard care.

11. Risks and Benefits

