Study Procedures and Assessments	
Data will be collected as follow:
 
Baseline
 
Demographics at Baseline: age, gender. Medical history at Baseline: HbA1c, Previous treatment, Name of the last pump device, Date of the first pump treatment, Number of severe hypoglycemia events in the last year, years since diagnose of T1D; DTSQs; DQoL; HFS. Auto Mode Activation at Baseline: Auto Mode activation date At the end of the run-in period, the following data will be also collected: Mean TIR (70-180mg/dL); Mean Time spent of sensor glucose value below 70mg/dL and below 54mg/dL; Mean Time spent of sensor glucose value above 180mg/dL and above 250mg/dL; Number of bio-chemical hypoglycemic event per week.
 
6M
 
DTSQs and DTSQc; DQoL; HFS; Diabetes parameters via CareLink™ Personal for Clinical Research: TIR; Mean time spent of sensor glucose value below 70mg/dL and below 54mg/dL; Mean time spent of sensor glucose value above 180mg/dL and above 250mg/dL; Number of bio-chemical hypoglycemic event per week; HbA1c Number of severe hypoglycemia; Use of Auto Mode; Use of CGM; Number of Auto Mode outings.
 
12M
 
DTSQs; DQoL; HFS; Diabetes parameters via CareLink™ Personal for Clinical Research: TIR;

---	--

	
Mean time spent of sensor glucose value below 70mg/dL and below 54mg/dL; Mean time spent of sensor glucose value above 180mg/dL and above 250mg/dL; Number of bio-chemical hypoglycemic event per week; HbA1c Number of severe hypoglycemia; Use of Auto Mode; Use of CGM; Number of Auto Mode outings.
 
Device data (insulin/CGM) will be collected throughout the study period and evaluated at every 3month.

Safety Assessments	Post-Market surveillance applies only. Adverse Events and Device Deficiencies are not collected. This is an efficacy and Quality of Life and treatment satisfaction non-interventional study. Complaint reporting will be done as per local requirements and Medtronic processes, including vigilance for commercially approved products.

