10.3. Enrollment/baseline visit

The investigational center will not initiate any subject activities until EC approval (and all necessary approvals) has been granted. The investigator will check the study eligibility based on a patient meeting, all the study inclusion criteria and none of the exclusion criteria. Investigator will inform the patient about the study and will provide him/her the EC approved Data Release Form. After subjects having given their written Date Release consent, they are considered enrolled in the study and the following information will be collected:

Baseline:

- Demographics
 - Age, sex
- Medical history
 - HbA1c (available value collected up to 30 days before enrollment can be used)
 - Previous treatment
 - Name of the last pump device

- Date of the first pump treatment
- Years since diagnose of T1D
- Number of severe hypoglycemia in the last year

Severe Hypoglycemia is an event requiring assistance of another person, due to altered consciousness, to actively administer carbohydrate, glucagon, or other resuscitative actions. This means that the subject was impaired cognitively to the point that he/she was unable to treat his or herself, was unable to verbalize his or her needs, and was incoherent, disoriented and/or combative.

- Questionnaires
 - DTSQs
 - DQoL (except for patients between 7 and 12 years old)
 - HFS

The questionnaires will be completed following the specific, standardized instructions in the waiting room and returned the same day. Paper versions of the questionnaires will be made available for this purpose.

To minimize any bias, subjects will fill out the questionnaire before they get equipped by the MiniMed™ 780G insulin pump, before clinician assessments and discussion of their clinical condition, and any other related topics that could influence patient's perception and feelings prior to responding to the questions.

Once eligibility has been confirmed, subject will start a run-in phase in a hospital outpatient setting, as per standard practice of the site.

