The objective of the run-in phase is to train the subjects on the MiniMed™ 780G insulin pump, assess subjects' compliance and ability to comprehend the study procedures and tolerance of wearing the sensor and transmitter continuously. It is expected that during the run-in phase the MiniMed™ 780G insulin pump will be set in Manual mode and all the algorithms are switched off, and baseline CGM data will be collected. Data from the MiniMed™ 780G insulin pump will be uploaded in the CareLink™ Personnel for Clinical Research as per standard practice before Auto Mode activation.

Baseline CGM data are listed below:

- Mean TIR (70-180mg/dL)
- Mean Time spent of sensor glucose value below 70mg/dL and below 54mg/dL
- Mean Time spent of sensor glucose value above 180mg/dL and above 250mg/dL
- Number of bio-chemical hypoglycemic event per week

Bio-chemical hypoglycemic events are defined as events with sensor glucose values lower than 54 mg/dL for more than 15 min consecutively.

The expected duration of the run-in phase is approximately 2 weeks. At the end of the run-in phase the MiniMed™ 780G insulin pump will be set in Auto Mode and the date of activation will be collected, and identified as a start of the study phase.

10.4. 6- and 12-month Follow-up Visits

Subsequent follow-up visits will be performed according to the therapy management standard of care at 6 and 12 months after Auto Mode activation in the study.

During the follow-up visits, patients will be asked to fill-out the following questionnaires:

Table 4: Questionnaires to be completed

	6 Month FU	12 Month FU
DTSQs	✓	✓
DTSQc	✓	
DQoL	✓	✓
HFS	✓	✓

All questionnaires have been designed for self-completion. When available (e.g. DTSQ and HFS), specific version of the questionnaires will be completed by a parent for subjects younger than 13 years old. DQOL will not be administered in case patient is between 7 and 12 years old. Patient questionnaires are in a paper form and should be completed on site during routine follow-up visits. It is recommended to administer the DTSQs before the DTSQc.

Patients are followed per standard of care, therefore there are no mandatory visit windows defined in this study, however the visit windows defined below are provided as recommendation and guidance.

- 6 Month FU: Follow-up Office Visit - 180 Days (\pm 45 days)
- 12 Month FU: Follow up Office Visit - 365 Days (\pm 45 days)

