Data from the MiniMed™ 780G insulin pump will be uploaded in the CareLink™ Clinical for Research as per standard practice. The following data from the CareLink™ will be used to correlate with the QOL data:

- Mean TIR (70-180mg/dL)
- Mean Time spent of sensor glucose value below 70mg/dL and below 54mg/dL
- Mean Time spent of sensor glucose value above 180mg/dL and above 250mg/dL
- Number of bio-chemical hypoglycemic event per week
- Number of severe hypoglycemia,
- Time in Auto Mode,
- Time in CGM,
- Number of Auto Mode outings.

Additionally, the following information will be collected at each visit:

- HbA1c (available value collected \pm 30 days from 6-month and 12-month follow up visits can be used).

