10.5. Study Exit

A study exit form will be completed for all included subjects. Per normal study completion, the date of the last follow up visit, the 12-month Follow-up visit, will correspond to the study exit date. At the end of the study, the subjects will continue to be treated following the routine practice of each center and physician's discretion.

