7.1.3. Analysis Sets

The following subject sets will be used for the analysis:

- The Intention To Treat (ITT) includes all patients enrolled in the study with signed Data Release Form, fulfill the inclusion and exclusion criteria. The ITT will be used for all endpoints and safety evaluation.
- The Per Protocol (PP) includes all patients enrolled in the study with signed Data Release Form, fulfill the inclusion and exclusion criteria and having at least 70% of time using the Auto Mode during the 6-month follow up. The PP set will be used for all endpoints.

The primary analysis will be performed on the ITT set. As sensitivity analysis the PP set will be used. The following table shows how each population set will be used for analyses:

Population set	Baseline assessment	Primary Endpoint	Secondary Endpoints	Adverse Events
PP	✓	✓*	✓	
ITT	✓	✓	✓	✓

* The primary endpoint on the PP population will be considered as sensitivity analysis

For patients who dropout, the analyses will include all data up to the point of their last data collection.

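### No severe hypoglycaemia count is specified at early exit, so events after the last attended visit may be missing from the number reported under SAP 7.10

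*Protocol*

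**What the plan says.** **When the item is collected.** The baseline medical history in Protocol 10.3 includes "Number of severe hypoglycemia in the last year", which is a look-back over the time before enrolment. On study, the synopsis lists under both 6M and 12M "HbA1c Number of severe hypoglycemia; Use of Auto Mode; Use of CGM; Number of Auto Mode outings", and Protocol 10.4 repeats the item for the follow-up visits. Table 4 in Protocol 10.2 plans the follow-up form A_FU at 6 and 12 months only.

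**What happens at exit.** Protocol 10.5 states: "A study exit form will be completed for all included subjects". For completers the 12-month visit date is the exit date. For early exit, Protocol 10.11 requires that "the date, circumstances and the reason for termination must be documented both in source documents and on the appropriate eCRF". It defines no early-exit visit. It also provides that "Subjects may also be withdrawn from the study at the discretion of the Investigator if the patient's well-being is jeopardized by continuation of the study". For subjects who cannot be reached, the personal physician may be asked about safety and vital status, but 10.11 requires only the contact efforts to be documented.

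**What is reported.** Protocol 10.8 rules out collecting adverse events. SAP 7.10 nevertheless reports the number of severe hypoglycaemia events by summary statistics, without a time-at-risk denominator. On dropouts, SAP 7.1.3 says: "For patients who dropout, the analyses will include all data up to the point of their last data collection".

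**The concern.** Severe hypoglycaemia is the only clinical event that SAP 7.10 reports, and there is no adverse event form behind it. As the text stands, a subject who attends enrolment and leaves before the 6-month visit has no specified on-study record of this item. A subject who leaves between the two visits has none after the 6-month visit.

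The loss may not be random. Subjects can be withdrawn for their well-being, and Protocol 11.1 lists hypoglycaemia, seizure and coma among the potential risks of the system. A severe event is a plausible reason to leave. If it is, the reported number leans towards subjects who stayed, and it understates risk in a report that goes to the French health authority in support of reimbursement (Protocol 4.2 and 14.7.4).

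Device uploads do not fill the gap. Protocol 10.4 lists the item among the CareLink data, but the definition in 10.3 rests on altered consciousness and help from another person. A pump or sensor does not record that, so someone has to ask.

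**Working it through.** **Inputs from the documents.** Protocol 12.2: 245 pairs, 20% attrition, 306 enrolled. These reproduce. With SD 16 and correlation 0.5, the SD of the difference is 16 × √(2 × (1 − 0.5)) = 16. A one-sided 5% paired t-test with 90% power for 3 points needs 245 pairs, and 245 / 0.8 = 306.25. Planned attrition is then 0.20 × 306 = 61.2, or 61 subjects. That is an upper bound for early leavers, because the allowance also covers subjects below 70% Auto Mode use.

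**Assumptions, because the documents give neither event rates nor exit times.** 5%, 10% or 20% of 306 leave early (15, 31 or 61). Exits are even over months 0 to 6, so leavers contribute on average 3 months (0.25 year) and none of it is counted. Stayers contribute one year each. The event rate in leavers is r times that in stayers, with r = 1 or 3. The run-in of about two weeks is left out; including it would raise the shares slightly.

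**Formula.** With L leavers and S = 306 − L stayers, the stayers' event rate cancels:

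missed share = r × 0.25 × L / (S + r × 0.25 × L)

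| L | S | 0.25 × L | Missed, r = 1 | Missed, r = 3 |
|---|---|---|---|---|
| 15 | 291 | 3.75 | 3.75 / 294.75 = 1.3% | 11.25 / 302.25 = 3.7% |
| 31 | 275 | 7.75 | 7.75 / 282.75 = 2.7% | 23.25 / 298.25 = 7.8% |
| 61 | 245 | 15.25 | 15.25 / 260.25 = 5.9% | 45.75 / 290.75 = 15.7% |

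**Sensitivity to exit timing, 61 leavers.**
- Exits even over 12 months: about 30 subjects have no follow-up form, and 15.25 of 275.5 person-years are uncounted (5.5%).
- All exits evenly after an attended 6-month visit: 15.25 / 290.75 = 5.2% uncounted. Two thirds of the leavers' own time is still covered.
- All exits at month 6 with no 6-month form, as an extreme: 30.5 / 275.5 = 11.1% at equal rates, and 91.5 / 336.5 = 27.2% at a threefold rate.

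**The case against.** Several points on the other side stand.

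- **The exit form is not visible.** Protocol 14.2 places the eCRF copies under separate cover, so A_EXIT may already hold the item. The circumstances and reason for exit could also mention a severe event, and SAP 7.1.1 reports reasons for non-participation where known. A reason is not an event count, however, and SAP 7.10 does not draw on it. What can be said is that no count is specified.
- **Visits are flexible.** Protocol 10.4 sets no mandatory windows, and the suggested 6-month window opens at day 135 (180 − 45). A last contact near that time could serve as the 6-month visit.
- **The stakes are limited.** The item belongs to no primary or secondary endpoint, it is only described, and vigilance runs outside the study. CareLink uploads are expected about weekly, so sensor glucose below 54 mg/dL remains available for leavers up to their last upload.
- **The link between exit and event is plausible, not established.** The withdrawal rule speaks of well-being and does not name hypoglycaemia.

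Two stronger readings are tempting. A reader might infer that events in anyone who leaves early are never counted. The documents do not support this: events recorded at an attended 6-month visit are kept.

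A reader might also work with a risk per patient, say 5% in stayers and 15% in leavers. With 61 leavers, 9.15 / (12.25 + 9.15) = 42.8% of affected patients would be missed. But that gives leavers three times the full-year risk within an average of 3 months, or about 12 times the event rate. Nothing in the documents supports such a rate.

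**Conclusion.** The gap is real and narrow. Following the written plan, severe hypoglycaemia between the last attended visit and early exit has no specified place in the count under SAP 7.10. If exits are even over months 0 to 6, the missed share is about 1% to 6% at equal event rates and about 4% to 16% at a threefold rate in leavers. The top of each range uses the 61-subject upper bound. The rate ratio, the numbers leaving and their timing are assumptions. The likely direction is an understatement of risk. Completers lose nothing, and no primary or secondary endpoint changes. This is a cheap improvement to a descriptive safety figure; it does not threaten the study's main result.

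**What to change.** 1. **Exit form.** Add to A_EXIT, if it is not already there, the number of severe hypoglycaemia events (Protocol 10.3 definition) since the last recorded visit, up to withdrawal of consent. Name the item for early exits in Protocol 10.5, 10.11 and Table 3. If the form already holds it, only the text needs to change.
2. **SAP 7.10.** Count events from A_FU and A_EXIT together and report them per person-time, using the exposure already derived in SAP 7.7. That exposure runs to study exit, so for a subject with no exit count, end the person-time at the last visit where the count was taken.
3. **Optional.** Showing run-in events apart from Auto Mode events would need an event date or a split field on both forms. A single count cannot separate them.

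**Cost.** A small eCRF and protocol change with its ethics notification, and a sentence or two in the SAP. No visit or procedure is added. The count stays incomplete for subjects who cannot be reached. Because 10.11 bars recording data obtained after consent is withdrawn, the question has to be answered by that point.

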11.1. Potential Risks

The study aims to evaluate the effect on glycemic control, treatment satisfaction and the impact on the quality of life of patients using the MiniMed™ 780G System following the standard care in France. There are no expected additional risks relative to participation in this study as devices used are commercially available and used in accordance with approved labelling.

Furthermore, the study is non-interventional, subjects are treated according to standard clinical practice, therefore there are no additional risks associated with study participation.

Potential risks associated with the use of MiniMed™ 780G System include, but are not limited to the following list:

- Hypoglycemia
- Hyperglycemia
- Diabetic Ketoacidosis
- Seizure
- Coma
- Death

General risks related to insulin pump infusion set may include:

- Localized infection
- Skin irritation or redness
- Bruising
- Discomfort or pain
- Bleeding
- Irritation
- Rash
- Occlusions that can interrupt insulin delivery and lead to hyperglycemia or Diabetic Ketoacidosis

General risks related to sensor use may include:

- Skin irritation or other reactions
- Bruising
- Discomfort
- Redness
- Bleeding
- Pain
- Rash

- Infection
- Raised bump
- Appearance of a small "freckle-like" dot where needle was inserted
- Allergic reaction
- Fainting secondary to anxiety or fear of needle insertion
- Soreness or tenderness
- Swelling at insertion site
- Sensor fracture, breakage or damage
- Minimal blood splatter associated with sensor needle removal
- Residual redness associated with adhesive, tape, or both
- Scarring

Specific risks related to sensor use:

Use of medications with paracetamol, including, but not limited to fever reducers or cold medicine, while wearing the sensor may falsely raise sensor glucose readings and result in an over-delivery of insulin. The level of inaccuracy depends on the amount of paracetamol active in the body and may be different for each person.

Risks related to meter use:

- See the user guide that came with the device for the most current risks.

General risks related to serter use may include:

- The serter contains small parts and may pose a choking hazard that can result in serious injury or death.
- Side effects include discomfort and skin irritation at the insertion site.

11.2. Risk Minimization

The potential risks associated with the MiniMed 780G system were identified and have been successfully mitigated and are addressed in the user guide. There are no expected additional risks relative to participation in this study as devices used are commercially available and used in accordance with approved labelling. Any potential risks associated with this study are further minimized by selecting qualified investigators and training study personnel on the CIP.

Specific risks minimizations related to sensor use include, but are not limited to:

- Use of medications with paracetamol: if paracetamol is taken, stop the use of the medication before using SG readings to make treatment decisions. Use additional BG meter readings to verify glucose levels, turn off the Auto correction feature, and consider turning off the SmartGuard feature. Check the label of any medication to confirm whether paracetamol is an active ingredient.
- Do not use SG values to make therapy treatment decisions while the pump is in Manual

mode. SG values can only be used to make therapy treatment decisions while the SmartGuard feature is active. SG and BG values may differ. If the SG reading is low or high, or there are symptoms of low or high glucose, confirm the SG reading with a BG meter prior to making therapy decisions to avoid hypoglycemia or hyperglycemia.

- For persons seven to thirteen years of age, sensor insertion is approved for in the abdomen and buttocks. Do not insert the sensor into any other location.
- For persons fourteen years and older, sensor insertion is approved for the abdomen and back of the upper arm. Do not insert the sensor into any other location.

11.3. Potential Benefits

Subjects' participation in this study may offer no additional benefits in respect to the same treatment provided outside of the trial. Participation in this study will help in contributing to evidence-based medicine and in releasing data to support product reimbursement and utilization in France.

11.4. Risk-Benefit Rationale

Subjects are not put at any additional risk for participating in the study, as compared having the MiniMed™ 780G System treatment as part of their routine care.

The probable benefits of the device are based on data collected in several clinical research studies as described in section 4.1 Background. These data are and were used to support regulatory approval of the MiniMed™ 780G System in the United States and in Europe.

Participation in this study will help in contributing to evidence-based medicine and in releasing data to support product reimbursement and utilization in France.

12. Statistical Design and Methods

12.1. Sample size justification

The primary endpoint is to evaluate if the MiniMed™ 780G therapy in Auto Mode increases the proportion of Time In Range (TIR) at 6 months compared to the MiniMed™ 780G therapy in manual mode at baseline. The endpoint is the Time In Range (TIR) defined as the proportion of sensor glucose concentration within the target range 70-180 mg/dL (3.9-10.0 mmol/L).

The Pivotal study [12, 13] enrolled adolescents (ages 14–21 years) and adults (ages 22–75 years) with type 1 diabetes in a multicenter pivotal trial. The Medtronic MiniMed™ 670G system was used during a 2- week run-in phase without HCL control, or Auto Mode, enabled (Manual Mode) and, thereafter, with Auto Mode enabled during a 3-month study phase. The study has shown a significant

improvement on TIR of 60.4% (10.9%) to 67.2% (8.2%) in adolescents and from 68.8% (11.9%) to 73.8% (8.4%) in adults. Using this information and considering that this study is expected to include around 32 sites and including also patients aged >7 years old, a lower increase of TIR and higher variability are expected. The following assumptions were made:

- Improvement in TIR of at least 3% points at 6 months compared to the baseline.
- Standard deviation as 16% due to the mixed population and multiple sites expected for this study.

